Aim 1 Power. To illustrate power, MDE was estimated for proportion of Latinx tested per capita Latinx population with 1000 replications. One advantage of *Mplus* is the ability to specify events per month according to the design in which 10 census-located sites from Phase 1 will be conducting 20 events per month; and in the other study arm, 4 events per month will be conducted via community partner-located sites. Additionally, the group contrast for location type is simulated according to the clustering design with the appropriate allocation (mean = .42 and variance = .25). Residual variance of number of tested Latinx was specified at .7 for level 1 and .5 for level 2 in order to estimate an intra-class correlation (ICC) of .40, a conservative parameter reflecting the site level ICC from the preliminary analyses ranging from .24 to .37 for the related Latinx testing outcomes described in the preliminary studies section. Covariate parameters were entered with and effect size (ES) of .30 for historical week, and .19 for site characteristics at level 2 with .91 coverage. Models showed that the study is powered .81 to minimally detect an ES of .50, a medium effect.

Aim 2 and Aim 3 Analyses

Both Aim 2 and Aim 3 analyses will focus on the individual unit of analysis. Aim 2 will evaluate whether Phase II implementation fidelity of the *Promotores de Salud* health intervention will improve testing, reduce vaccination hesitancy, and increase vaccine acceptance and health literacy. Aim 3 will focus on the social determinants of pre-post change in the likelihood of vaccination, repeated tested for those unvaccinated, and reduced vaccine hesitancy. Both Aims will be specified as within-intervention group pre-post change. In general, we will estimate pre-post linear mixed models for vaccine hesitancy and generalized linear mixed models for increased testing counts and vaccine acceptance.

Using vaccination as an outcome, both Aims 2 and 3 are formally represented as a multilevel Bernoulli logistic model predicting the likelihood of vaccination:

$$\begin{aligned} \text{Level 1: } \text{Prob}(\text{Vaccine}=1) &= \Phi \\ \text{Log}[\Phi/(1-\Phi)] &= \beta_0 + \beta_1(\text{BL Vaccine Status}) + \beta_2(\text{Social Determinants}) + \beta_3(\text{Historical Week}) + r \end{aligned}$$

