$$\begin{aligned} \text{Level 2: } \beta_0 &= \gamma_{00} + \gamma_1(\text{Fidelity of Implementation}) + \gamma_2(\text{Location Contrast}) \dots \gamma_n(\text{Site Charateristics}) + u_0 \\ \beta_1 &= \gamma_{10} + u_1 \\ \beta_2 &= \gamma_{20} + u_2 \\ \beta_3 &= \gamma_{30} + u_3 \end{aligned}$$

$$\text{Mixed Model: } \text{Log}[\Phi/(1-\Phi)] = \gamma_{00} + \gamma_{01}(\text{Fidelity}) + \gamma_{02}(\text{Location Contrast}) + \gamma_{03}(\text{Site Characteristic}) + \gamma_{10}(\text{BL Vaccine Status}) + \gamma_{20}(\text{Social Determinants}) + \gamma_{30}(\text{Historical Week}) + u_0 + u_1 + u_2 + u_3 + r$$

Where the probability of getting vaccinated Φ is regressed on level 1 baseline vaccine status β_1 , which then estimates the change in vaccine status from pre- to post-*Promotores*. Aim 2 fidelity of implementation is then estimated at level 2 as γ_1 controlling for location type and site level characteristics. Aim 3 social determinants are estimated at level when shown here as β_2 .

Aims 2 and 3 Power. For the multilevel model addressing aims 2 and 3, based on our preliminary Phase I data, we expect a total of 1650 survey participants over 11 months (200 tests per month via census-located events and 100 tests per month in partner-located events, for a total of 300 tests/month, with a 50% enrollment rate into the survey \times 11 months). For the one-month follow-up we anticipate a 50% retention rate. For a total of 825 pre-post participants. Power was estimated using a two-level Monte Carlo simulation, with the ability to model pattern missingness via both location approaches. To be conservative a retention rate was estimated at .50 for the established Phase I location approaches which will include a higher frequency of events, and a retention of .40 was estimated as the missing data pattern for Phase II partner-located; moreover, the proportion of missing data patterns were specified using the proportional design allocation and an ICC of .30 for individual testing outcomes. The proposed study is powered .81 to detect a MDE of .32 for fidelity of implementation at level 2, and is powered .83 to detect an MDE of .11 for social determinant variables at level 1 with .92 coverage.

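### The SAP reads the coefficient on baseline vaccine status as pre-post change, which it does not measure; if status means 'ever vaccinated', that coefficient and its site random slope cannot be estimated by maximum likelihood

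*SAP*

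**What the plan says.** SAP section 4.3, under 'Aim 2 and Aim 3 Analyses', sets the design: "Both Aims will be specified as within-intervention group pre-post change". The first outcome named for Aim 3 is vaccination: "Aim 3 will focus on the social determinants of pre-post change in the likelihood of vaccination". One equation is given for the two aims: "Using vaccination as an outcome, both Aims 2 and 3 are formally represented as a multilevel Bernoulli logistic model predicting the likelihood of vaccination".

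At level 1 the log odds of Vaccine = 1 depend on baseline vaccine status (beta_1), social determinants (beta_2) and historical week (beta_3). At level 2 beta_1 is a fixed part plus a site deviation u_1. There is no pre/post time term. The explanation begins "Where the probability of getting vaccinated" and says of the baseline-status term: "which then estimates the change in vaccine status from pre- to post". It then turns to the effects that carry the aims. For Aim 2, "Aim 2 fidelity of implementation is then estimated at level 2", as gamma_1; Aim 3 is assigned to beta_2.

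The power paragraph for these aims expects 1650 survey participants and 50% retention: "For a total of 825 pre-post participants". It uses an ICC of .30, labelled as being for individual testing outcomes. It reports power .81 for an effect of .32 (fidelity) and .83 for an effect of .11 (social determinants).

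The text supplied does not define vaccine status or restrict this model to people not yet vaccinated. Survey eligibility (Protocol section D) has no vaccination criterion. The SAP phrase "repeated tested for those unvaccinated" attaches to repeat testing, not to the vaccination model.

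**The concern.** A coefficient on the baseline value of an outcome measures how strongly follow-up depends on baseline. It does not measure how far the outcome moved. An analyst who followed the SAP's sentence would report beta_1 as the pre-post change in vaccination, and the number could move the opposite way to uptake.

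There is also a conditional problem. If the status cannot be lost, no participant can be vaccinated at baseline and unvaccinated a month later. That cell is empty by definition, and the model asks for a coefficient, and its variation between sites, that the data cannot supply. The sample that informs the Aim 2 and Aim 3 effects for this outcome would then be smaller than the pre-post total used for power.

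**Working it through.** **1. The SAP's sample size.** 300 tests/month × .50 × 11 = 1650, and 1650 × .50 = 825. Both reproduce. The retention rates in the simulation (.50 and .40 by location) imply 1100 × .50 + 550 × .40 = 770.

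**2. What beta_1 measures when outcome and covariate are the same status.** Let p1 and p0 be the follow-up probabilities among those vaccinated and unvaccinated at baseline. Ignoring the other terms, beta_1 = logit(p1) − logit(p0). Net change = (coverage × p1 + (1 − coverage) × p0) − coverage. All inputs are assumed.

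| Baseline coverage | p0 | p1 | Net change | beta_1 |
|---|---|---|---|---|
| 50% | .2 | .8 | 0 | 2.77 |
| 50% | .5 | .5 | 0 | 0 |
| 20% | .3 | .9 | +22 points | 3.04 |
| 80% | .3 | .9 | −2 points | 3.04 |

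Equal change goes with different beta_1, and equal beta_1 with different change. With p1 = .99, p0 = .05, .10, .20 and .40 give beta_1 = 7.54, 6.79, 5.98 and 5.00. The fall depends on holding p1 fixed: moving from (p1, p0) = (.90, .05) to (.99, .10) raises beta_1 from 5.14 to 6.79.

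**3. If the outcome is a dose between surveys.** beta_1 then compares the baseline groups. If 5% of both groups are dosed, or 20% of both, beta_1 = 0 either way.

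**4. If status is 'ever vaccinated'.** Then p1 = 1 and logit(p1) is infinite.
- Single-level fits to 825 simulated records (coverage 30–70%, uptake 5–20%): beta_1 rose by 1 per iteration without converging. At 50% coverage and 10% uptake it was 13.4, 18.4, 23.4 and 28.4 at iterations 10, 15, 20 and 25.
- Two-level likelihood (18 sites of 46, assumed): it levelled off at −173.6971 for a fixed part of 20 and 30, identically for random-slope SD 0, .5, 1 and 2. Neither quantity is identified.
- Fidelity and social-determinant coefficients: .525 (SE .154) and .601 (SE .145), the same in all 825 records and in the 406 unvaccinated at baseline.

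**5. Misreporting, under 'ever vaccinated'.** Let q1 be coverage, q0 = 1 − q1, u uptake, m the misreporting rate among the truly vaccinated (unrelated to covariates), and A = q0·u(1 − u). Approximate ratios of the estimated to the true coefficient:
- Error at follow-up only, full model: A / [A + q1·m(1 − m)]. The restricted model is not affected.
- Error at baseline only, restricted model: A / [n·p(1 − p)], with n = q0 + q1·m and p = (q0·u + q1·m)/n.

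| q1, u, m | Follow-up error, full model | Baseline error, restricted model |
|---|---|---|
| .5, .10, .01 | .045/.04995 = .90 | .92 |
| .5, .10, .03 | .045/.05955 = .76 | .79 |
| .8, .05, .01 | .0095/.01742 = .55 | .58 |
| .8, .05, .03 | .0095/.03278 = .29 | .33 |

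Large simulated single-level logistic fits for the last column gave .90–.92, .79–.80, .57–.58 and .32–.36. Restriction therefore removes the first kind of error but not the second.

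**6. Informative sample under 'ever vaccinated'.** At assumed coverage of 20, 50 and 80%, 825 × (1 − coverage) is about 660, 412 and 165. On 770 it is 616, 385 and 154.

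**The case against.** The best defence is that the sentence loosely describes the whole regression. Adjusting for baseline is ordinary, and the protocol (end of section D) plans analysis of covariance with pre-post scores. On that reading the model is sound unless the status cannot be lost. The sentence still needs correcting, because it attaches the change to the baseline-status term and describes fidelity and social determinants separately.

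A second defence stands: the SAP assigns no aim to beta_1. Aims 2 and 3 rest on gamma_1 and beta_2, which survive.

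Third, the separation problem depends on a definition that the supplied text lacks. The SAP also names vaccine acceptance as an outcome, and acceptance can be reversed. A definition may lie in parts of the SAP not supplied.

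Three stronger readings are tempting, but the documents do not support them:
- *That the Aim 2 and Aim 3 results would be invalid.* Without misreporting, the two target effects are the same in the full and the restricted model.
- *That restricting to the unvaccinated cures misreporting.* It removes inconsistent follow-up answers from people recorded as vaccinated. Vaccinated people recorded as unvaccinated at baseline enter the restricted set and look like new vaccinations.
- *That power for vaccination falls to a particular value.* Scaling the variance behind .11 by 825/N ignores events. At 80% coverage the 165 at risk would yield about 8 vaccinations at 5% uptake and 33 at 20%, yet the scaling gives one power for both.

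**Conclusion.** The point holds in a limited form and is worth fixing. That beta_1 is not the pre-post change is certain, and it does not depend on how vaccination is defined. Its fall with rising uptake assumes a fixed follow-up probability among the baseline-vaccinated.

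The failure of beta_1 and u_1 is conditional on a status that cannot be lost, and it concerns maximum likelihood. A penalised or Bayesian fit would return a finite value set by the penalty or prior, and a few inconsistent answers would give one set by error.

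The attenuation ratios show direction and possible size only, since coverage, uptake and misreporting rates are all assumed. The .32 and .11 effects should not be read as detectable effects for vaccination. The size of the loss cannot be derived, because the documents give no coverage, uptake or number of sites for this model. The primary testing outcome is not touched.

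**What to change.** - Delete the sentence that reads the baseline-status term as change.
- Define the vaccination status used, for example any dose, full series or booster.
- If the status cannot be lost, model reaching it by one month among participants who had not reached it at baseline, within the planned within-intervention design. Keep gamma_1 and beta_2; drop beta_1 and u_1. Say that misreported baseline status can still attenuate both effects.
- If the outcome is a dose between surveys or a reversible measure, keep baseline status as an adjustment covariate only.
- Keep baseline-adjusted models for the other outcomes.
- State that .32 and .11 do not apply to vaccination. Give its power on the expected number at risk, events, number of sites and an ICC for vaccination.

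The cost is SAP wording, possibly a restricted model for one outcome, and one new power statement. No new data are needed. The downside, where restriction applies, is a smaller stated informative sample and a less favourable detectable effect for vaccination.

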4.3 Statistical Design and Power

A power convention of .80 and for an alpha level of .05 was chosen for evaluating the multilevel model for the proposed site level outcomes (Aim 1) and for the individual level outcomes (Aim 2 and Aim 3). The minimally detectable effect size (MDE) was estimated using Monte Carlo simulation with 1000 replications in *Mplus* 8.5. An advantage of the Monte Carlo simulation approach is the ability to estimate parameter bias, standard errors, and coverage of confidence intervals.

Figure 4.3.1 Phase II Study Design and Expected Sample Sizes by Unit of Analysis

Aim 1 Analyses

Converting the Odds Ratio from the site level preliminary studies and the per capita outcomes Cohen's d ranged from .45 to .60, medium effects. The primary outcome for Aim 1 will be the number of Latinx tested specified as a generalized linear multilevel Poisson model for the count model and as a general linear model for the per capita proportional measures. For Aim 1 analyses, the unit of analysis is the number of total events nested within site. Across the continuing Phase I and the proposed Phase II testing events, there will be a total of 24 events per month for a total of 11 months (264 events).

As an illustration of total number tested, formally, the primary generalized linear model will be the following:

$$\text{Level 1: } E(\text{Test Count}) = \lambda \\ \text{Log}[\lambda] = \beta_0 + \beta_1(\text{Historical Week}) + r$$

$$\text{Level 2: } \beta_0 = \gamma_{00} + \gamma_1(\text{Location Contrast}) \dots \gamma_2(\text{Site Characteristics}) + u_0 \\ \beta_1 = \gamma_{10} + u_1$$

$$\text{Mixed Model: } \text{Log}[\lambda] = \gamma_{00} + \gamma_{01}(\text{Location Contrast}) + \gamma_{02}(\text{Site Characteristics}) + \gamma_{10}(\text{Historical Week}) + u_0 + u_1 + r$$

Where
the
expected
count of
Latinx
tested

represented as $\log \lambda$ is regressed on level 1 historical calendar week β_1 and the effect of the site-location outreach contrast γ_1 is estimated at level 2 as location type effect, controlling for socio-demographic census characteristics of each site γ_2 . Nested models will be compared and evaluated for over or under dispersion, zero-inflation, and normality for the linear mixed model estimating per capita Latinx tested.

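### The SAP's single level-1 power figure for Aim 3 (.83 at .11) cannot apply to retesting, which is limited to the unvaccinated, and probably does not apply to vaccination

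*SAP*

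**What the plan says.** SAP 4.3 sets the standard for all aims: "A power convention of .80 and for an alpha level of .05 was chosen", with effects estimated by "Monte Carlo simulation with 1000 replications".

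Under Aims 2 and 3 Power, the sample is built up as follows: "we expect a total of 1650 survey participants over 11 months", from "200 tests per month via census-located events and 100 tests per month in partner-located events", "with a 50% enrollment rate into the survey". Half are expected to return at one month: "For a total of 825 pre-post participants". The simulation text then uses retention of .50 at the Phase I locations and .40 at the partner locations, with an ICC of .30. For level 1 it reports one result: the study "is powered .83 to detect an MDE of .11 for social determinant variables at level 1 with .92 coverage".

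Under Aim 2 and Aim 3 Analyses, Aim 3 concerns the social determinants of "pre-post change in the likelihood of vaccination, repeated tested for those unvaccinated", and of reduced vaccine hesitancy. The worked model is a two-level logistic model for a binary vaccination status, with baseline vaccine status as a level-1 covariate and a site-level random slope on social determinants.

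**The concern.** The three Aim 3 outcomes do not share one analysable population. Everyone with follow-up can contribute to vaccine hesitancy. Only people unvaccinated at baseline can contribute to retesting, by the SAP's own definition. Only they can become newly vaccinated, if status is ever/never. Baseline vaccine status is useful as a covariate only if it varies, so the unvaccinated share must be below 1. The visible sizing text takes nobody out for this reason.

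The risk lies in interpretation. A null result for social determinants on retesting or vaccination would be read against a stated power of .83, when the analysis may have rested on a much smaller group.

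**Working it through.** **Inputs from SAP 4.3.** 200 + 100 tests per month, 11 months, 50% enrolment; retention .50 overall, or .50/.40 by location; alpha .05 (sidedness not stated, two-sided assumed); power .83 at an effect of .11; convention .80. **Not given:** the share unvaccinated at baseline (called f here), the N actually simulated, and, for this simulation, the residual variance, number of sites, slope variance and outcome prevalence.

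**Step 1: the sample.** 300 x .50 x 11 = 1,650, and 1,650 x .50 = 825, both as stated. With the simulated retention: 200 x .50 x 11 x .50 + 100 x .50 x 11 x .40 = 550 + 220 = 770. That 825 or 770 was the simulated N is an inference from this text.

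**Step 2: the .83.** It cannot be uniquely reproduced from the inputs given. The simplest formula, power = Phi(.11 x sqrt(n) - 1.96) with residual variance 1, gives .885 at n = 825 and .863 at n = 770. Two-level simulations with a random slope, under several assumed variances and numbers of sites, gave about .59 to .89. So .83 is plausible for the full 770 to 825.

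**Step 3: who carries information.** For retesting, vaccinated participants are excluded by definition. For an ever/never vaccination status, everyone vaccinated at baseline is still vaccinated at follow-up. With baseline status in the logistic model, its coefficient absorbs them completely, and they say essentially nothing about the social-determinant coefficient. A simulated single-level example (800 people, half vaccinated) confirmed this: the social-determinant estimate was .120 with SE .105 whether the 400 vaccinated were kept or dropped.

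**Step 4: the loss as a function of f.** Take .83 as correct at f = 1. The implied SE is .11 / (1.960 + .954) = .11 / 2.914 = .0377. With SE proportional to 1/sqrt(n):

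- power at .11 = Phi(2.914 x sqrt(f) - 1.96)
- MDE at .80 power = (1.960 + .842) x .0377 / sqrt(f), that is, about .106 / sqrt(f)

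| f | n (of 770 / of 825) | power at .11 | MDE at .80 power |
|---|---|---|---|
| 1 | 770 / 825 | .83 | .106 |
| .90 | 693 / 742 | .79 | .111 |
| .70 | 539 / 578 | .68 | .126 |
| .50 | 385 / 412 | .54 | .150 |
| .30 | 231 / 248 | .36 | .193 |

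The .80 convention holds at .11 only if f is at least (2.802 / 2.914)^2, about .92: roughly 712 of 770 or 762 of 825.

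**Step 5: sensitivity of that scaling.**

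- *Simplest formula instead of the SAP's .83.* Power of .80 needs (2.802 / .11)^2, about 649 participants. That is 79% of 825 or 84% of 770, so more vaccinated participants could be tolerated.
- *Random slope.* Its variance depends on the number of sites and does not shrink with participants. As an illustration, assume residual variance .7 and n = 770. The residual part of SE^2 is .7 / 770 = .00091 out of .00142, and the rest is assigned to the slope. Power is then about .73 at f = .70 and .62 at f = .50, against .68 and .54 in the table.
- *Binary outcome.* For vaccination, power also depends on the proportion c who convert. Put .11 on the latent SD scale (log-odds .11 x pi / sqrt(3) = .1995), with SE = 1 / sqrt(770 x f x c x (1 - c)). At f = .50, power is about .50, .35 and .22 for c = 50%, 20% and 10%.

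**The case against.** The sizing arithmetic is right: 1,650 and 825 reproduce exactly, and .83 may be correct for vaccine hesitancy. The SAP never states the N it simulated, so one cannot say as a fact that the vaccinated were counted in. Figure 4.3.1 and the preliminary-studies section are not available, and either might give the vaccination share. If nearly everyone is unvaccinated, little is lost. Vaccine status is not defined, and if later doses count, some people vaccinated at baseline could still change. Aim 3 is also a pre-post analysis within the intervention group. The protocol's primary outcomes are site-level Latinx testing rates, so the randomised comparison does not depend on it.

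Most of this stands and limits how far the point can be pushed. It does not rescue the single figure for retesting: that outcome is restricted by the SAP's own wording, and the sizing text describes no matching restriction.

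A reader might infer more: that Aim 3 has only about even odds of detecting .11, or that two of its three outcomes are certainly underpowered. The documents do not support either. The first needs an unvaccinated share near one half, which appears nowhere. The second needs an ever/never definition of vaccination and a share low enough to matter.

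**Conclusion.** The point holds in a limited form: the power is stated for the wrong population. The .83 at .11 does not apply to retesting and probably not to vaccination. The direction is clear for retesting, since any vaccinated participant lowers the usable number below the full pre-post sample. For vaccination it rests on an ever/never reading of the binary status.

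The size is conditional on the missing share: from about .79 power at 90% unvaccinated to about .36 at 30%, assuming that .83 is right for the full sample and that the SE scales as 1/sqrt(n). A sizeable random-slope variance makes the loss smaller. For vaccination, a low conversion rate makes power lower still. This should be corrected, but it does not bear on the randomised primary comparison.

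**What to change.** In SAP 4.3, state the expected number unvaccinated at baseline with follow-up, taking the share from the Phase I surveys if they give it and otherwise showing a range. Say whether vaccination means ever/never or also counts later doses. Re-run the existing simulation on the at-risk number separately for retesting and for vaccination, with an assumed conversion rate for the latter, and report the MDE at .80 power for each. State the N used in each run. Limit the .83/.11 statement to outcomes analysed in all pre-post participants, such as vaccine hesitancy.

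The cost is a simulation re-run and a text edit. The downside is a less favourable stated MDE for two outcomes. No change to enrolment is proposed.
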